4.3 Withdrawal Criteria

Patients may be discontinued from study drug for any of the following reasons:

- The patient no longer meets all inclusion criteria or meets any exclusion criteria and is found to be ineligible for participation through procedures (eg, medical examinations) performed after Randomization.
- Occurrence of any medical condition or circumstance that exposes the patient to substantial risk and/or does not allow the patient to adhere to the requirements of the protocol.

- Any SAE, clinically significant adverse event, severe laboratory abnormality, intercurrent illness, or other medical condition that indicates to the Investigator that continued participation is not in the best interest of the patient.
- Pregnancy.
- Requirement of the following therapy:
 - CMV hyperimmune globulin (eg, CytoGam®).
 - IVIg.
 - Plasmapheresis.
- Patient failure to comply with protocol requirements or study-related procedures and the Investigator considers it inappropriate to administer the study drug.
- Initiation of Rescue Phase.

Patients who discontinue study drug for any reason should be followed per the study schedule of events until the end of study participation.

Participation of a patient in this clinical study may be discontinued for any of the following reasons:

- The patient withdraws consent or requests discontinuation from the study for any reason.
- Termination of the study by the Sponsor or the regulatory authority.
- If a patient develops COVID-19 and is unable to continue with study visits and observations, the patient should be discontinued from the study and standard of care CMV treatment should be initiated, if necessary. If COVID-19 treatment will be provided to the patient, the Investigator should notify the Medical Monitor prior to study discontinuation, if possible. All patients should be followed for safety and resolution of COVID-19 infection. Patients who are able to complete study-related visits as an outpatient or via home healthcare services (United States only) or are inpatient and can receive study treatment will be allowed to continue to participate in the study if they do not receive any experimental treatments for COVID-19.

In the case of patients lost to follow-up, attempts to contact the patient must be made and documented in the patient's medical records.

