5.6 Prior and Concomitant Medications and/or Procedures

5.6.1 Excluded Medications and/or Procedures

The following anti-CMV therapies will be prohibited within 7 days prior to Randomization through the end of the study:

- Anti-CMV agents (eg, foscarnet, GCV, VGCV, letermovir, high dose acyclovir [≥ 500 mg/m² intravenously every 8 hours, 10 mg/kg intravenously every 8 hours or 800 mg orally 4 times a day], high dose valacyclovir [1000 mg orally 3 times a day], high dose famciclovir [500 mg orally every 8 hours], or cidofovir).

Note: The use of anti-CMV agents per local standard of care during the Rescue Phase of the study is permitted.

Note: The use of anti-HSV and anti-VZV prophylaxis for at-risk patients is recommended (as long as the doses are below the one specified above).

The following therapies will be prohibited within 28 days prior to Randomization through the end of the study:

- CMV hyperimmune globulin (eg, CytoGam®)
- IVIg
- Plasmapheresis (receipt prior to first study drug administration is acceptable)

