6.6 Rescue Phase

After first study drug administration, patients who develop detectable CMV disease (CMV syndrome [see Appendix C for definition of CMV syndrome] or tissue-invasive CMV disease [see Appendix D for definitions of CMV disease]) or CMV viremia (defined as the detection of ≥ 250 IU/mL in plasma measured by PCR analysis in central laboratory or meets the local criteria for CMV viremia measured by PCR analysis or antigenemia testing) can enter the Rescue Phase of the study and be treated by anti-CMV agents per local standard of care until the patient is negative for CMV viremia, has recovered from CMV disease, or up to Week 28, whichever comes first. When this rescue therapy is completed, the Rescue Phase is terminated at least 4 Study Weeks after the last study drug administration and all Week 28 procedures will be performed as per Section 6.7 Early Termination Visit and Withdrawal Procedures.

Note: Collection of blood samples for serum NPC-21 concentration measurement at Weeks 4, 8, and 12 during the Rescue Phase will be handled in the same manner as visits without study drug administration.

Note: If the patient is negative for CMV viremia or has recovered from CMV disease before 4 Study Weeks have passed following last study drug administration, weekly scheduled visits are not required. The Rescue Phase visits may be conducted by home healthcare services (United States only). The Rescue Phase procedures may be performed at the next scheduled visit after detecting CMV viremia or CMV disease with or without anti-CMV agents per local standard of care. Some Investigators may prescribe anti-CMV agents (eg, VGCV) in advance and instruct the patient to start taking the drug as soon as possible for safety if the disease or viremia develops. If this is the case, the Rescue Phase procedures may be performed at the next scheduled visit.

The following procedures will be performed upon entering the Rescue Phase:

- Record the rescue in IRT.
- Record concomitant medications.
- Record the date and reason for entering the Rescue Phase.
- Perform complete physical examination.
- Collect blood sample for CMV DNA analysis by the central laboratory.
- Collect blood samples that will be stored for screening for resistant strains analysis.
- Perform EQ-5D-5L.
- Record adverse events.

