3.2.2 Modified Intent-to-Treat Population

The modified Intent-to-Treat (mITT) Population will include all patients who receive a kidney transplant from a living or deceased donor and receive at least 1 dose of study drug (6 mg/kg NPC-21, 12 mg/kg NPC-21, or placebo). The mITT Population will be used for all efficacy analyses.

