3.4.1 Primary Efficacy Analysis

The proportion of patients with the occurrence of CMV disease (CMV syndrome [see Appendix C of the protocol for definition of CMV syndrome] or tissue-invasive CMV disease [see Appendix D of the protocol for definitions of CMV disease]) or CMV viremia (defined as the detection of ≥ 250 IU/mL in plasma measured by PCR analysis in central laboratory or meets the local criteria for CMV viremia measured by PCR analysis or antigenemia testing) by Week 16 will be summarized by treatment group.

The 2-sided 95% exact Clopper-Pearson confidence intervals of the proportions will be provided. For any two treatment groups, the proportion difference and 95% unstratified Miettinen-Nurminen (score) confidence limits will be presented.

Comparisons across placebo and 6 mg/kg NPC-21 treatment group will use logistic regression analysis with stratification factor of region (United States or Japan) as a covariate

Non-responders will include all patients who develop CMV disease or CMV viremia. In principle, patients who discontinue from the study prior to Week 16 in the absence of CMV disease or CMV viremia will be considered as non-responders. If warranted under special circumstances, a patient who discontinues from the study prior to Week 16 may be discussed with the medical expert to determine status as a responder or non-responder. If this occurs, the rationale for considering the patient as a responder will be finalized before database lock and documented in this SAP. Sensitivity analysis may be performed to assess the impact of these patients on analysis results.

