2 DATA ANALYSIS CHANGES

2.1 Categorical Endpoints

In SAP version 1.0, section 3.4.2.1 describes that the categorical endpoints are analyzed using the same analysis method as the primary endpoint.

However, for the analysis of primary endpoint, the non-responders include all patients who develop CMV disease or CMV viremia and patients who discontinue from the study prior to Week 16 in the absence of CMV disease or CMV viremia.

This SAP addendum further clarifies that for the endpoints below, patients who discontinued from the study prior to Week 16 in the absence of CMV disease would not be considered as non-responders:

- Incidence of CMV disease by Week 16
- Incidence of CMV disease by Week 28

For the endpoints below, patients who discontinued from the study prior to Week 16 in the absence of CMV viremia would not be considered as non-responders:

- Incidence of CMV viremia by Week 16
- Incidence of CMV viremia by Week 28

For the secondary endpoint “Incidence of CMV disease or CMV viremia by Week 28”, the same analysis method as the primary endpoint is used by still including patients who discontinued from the study prior to Week 16 in the absence of CMV disease or CMV viremia as non-responders.

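### The primary analysis counts an event-free patient who starts a prohibited anti-CMV drug before Week 16 as a responder, so a non-study antiviral can be credited to the assigned arm, in either direction

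*SAP*

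**What the plan says.** **Who fails.** SAP 3.4.1 (and Protocol 10.2.1) names two groups. The first is "Non-responders will include all patients who develop CMV disease or CMV viremia". The second, as a default, is "patients who discontinue from the study prior to Week 16 in the absence of CMV disease or CMV viremia will be considered as non-responders". The default can be set aside case by case: "If warranted under special circumstances, a patient who discontinues from the study prior to Week 16 may be discussed with the medical expert". Section 2.1 of the SAP Addendum restates the primary rule with the same two groups: "the non-responders include all patients who develop CMV disease or CMV viremia and patients who discontinue from the study prior to Week 16".

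**Prohibited drugs.** Protocol 5.6.1 says: "The following anti-CMV therapies will be prohibited within 7 days prior to Randomization through the end of the study". It then lists ganciclovir, valganciclovir, letermovir and others, with an exception for the Rescue Phase.

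**Who is analysed.** SAP 3.2.2 says: "The mITT Population will be used for all efficacy analyses". Membership needs a transplant and one dose. SAP 3.1.5 analyses efficacy data as observed, without imputation.

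**After stopping study drug.** Protocol 4.3 says: "Patients who discontinue study drug for any reason should be followed per the study schedule of events until the end of study participation".

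**Per-protocol set.** SAP 3.2.3 lists restricted concomitant medication among the major deviations that may affect the primary assessment. SAP 3.4 repeats the primary endpoint in that set.

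**The concern.** The trial asks whether NPC-21 prevents CMV. A patient who takes an effective antiviral from another source and then has no recorded event shows little about the assigned arm, yet is counted as a success for it. The plan acknowledges that restricted medication can affect the primary assessment, but its only response is possible exclusion from a supportive set. That exclusion conditions on something that happened after randomisation and leaves the mITT result unchanged.

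At stake is the 6 mg/kg versus placebo difference, planned at 48 patients per arm, where a few patients can move the estimate. The misclassification could hide a real effect or enlarge an apparent one, and the choice of rule should not be made after the data are seen.

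**Working it through.** **1. The plan's own sample size.** Inputs from SAP 2.2.4: 60% versus 30%, 2-sided 0.05, 80% power, 15% discontinuation. With unpooled variance, n = (0.6×0.4 + 0.3×0.7)(1.960 + 0.842)² / 0.30² = 39.2, so 40, and 40/0.85 = 47.1, so 48. The stated 48 reproduces. The pooled-variance formula gives 42, inflated to 50. The sample size is not in dispute.

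**2. Where the patient falls.** Take a patient who starts a listed anti-CMV agent before Week 16, has no recorded event and stays in the study.

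- Event rule (SAP 3.4.1): not met.
- Drop-out rule (SAP 3.4.1): not met. The therapies that Protocol 4.3 names as grounds for stopping study drug are CMV hyperimmune globulin, IVIg and plasmapheresis. Even if study drug is stopped, follow-up continues.
- Rescue Phase (Protocol 6.6): entry requires CMV disease or viremia, so rescue patients are already failures. The gap covers only use without a recorded event.
- mITT (SAP 3.2.2): included.
- Optional sensitivity analysis (SAP 3.4.1): concerns patients who discontinued.

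The patient is therefore a responder. This follows from silence; no sentence says so.

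**3. Size.** The documents give no rate of such use, so a share u of 0 to 10% per arm is assumed. As a worst case, use is taken to suppress every event and to be unrelated to CMV risk. With planned event rate p:

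- rule as written: rate = (1 − u)p
- users counted as failures: rate = u + (1 − u)p
- power = Φ{[d − 1.96√(2p̄(1 − p̄)/n)] / √([p₁(1 − p₁) + p₂(1 − p₂)]/n)}, n = 48, where d is the difference and p̄ the mean of the two rates

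| Use, placebo / NPC-21 | As written: rates, difference, power | Users as failures: rates, difference, power |
|---|---|---|
| 0 / 0 | 60.0 vs 30.0, 30.0 points, 85.1% | same |
| 5% / 5% | 57.0 vs 28.5, 28.5 points, 81.6% | 62.0 vs 33.5, 28.5 points, 80.8% |
| 10% / 10% | 54.0 vs 27.0, 27.0 points, 77.8% | 64.0 vs 37.0, 27.0 points, 76.2% |
| 10% / 0 | 54.0 vs 30.0, 24.0 points, 66.8% | 64.0 vs 30.0, 34.0 points, 92.9% |
| 0 / 10% | 60.0 vs 27.0, 33.0 points, 91.6% | 60.0 vs 37.0, 23.0 points, 61.9% |

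**4. With drop-outs as failures.** The table ignores the plan's drop-out rule. With 15% drop-outs counted as failures, the rates are 0.15 + 0.85×0.60 = 66.0% and 0.15 + 0.85×0.30 = 40.5%, and power is 71.3%. Applying use among the remaining patients:

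- 10% in both arms: 61.7% as written, 62.8% with users as failures.
- 10% on placebo only: 51.6% and 82.3%.
- 10% on NPC-21 only: 79.5% and 48.8%.

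**5. Per patient.** One reclassified patient moves an arm's rate by 1/48 = 2.1 points. Take results near the planned rates, 29/48 on placebo and 14/48 on NPC-21. A logistic Wald test without the region covariate gives p = 0.0025. Reclassifying five NPC-21 patients as failures gives p = 0.043; six gives p = 0.068.

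**The case against.** **Use on suspicion is not described.** Protocol 6.6 says "Some Investigators may prescribe anti-CMV agents (eg, VGCV) in advance and instruct the patient to start taking the drug as soon as possible", and a reader might infer that the plan expects patients to hold an antiviral at home and start it early. The sentence goes on to make the start conditional on CMV disease or viremia having developed, and those patients are already failures. Early use on suspicion is an inference, not something the protocol foresees. This stands.

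**The endpoint catches most early treatment.** Viremia counts at 250 IU/mL or more centrally or on local criteria, with weekly sampling to Week 16. What remains is prohibited use with neither threshold met, which may be rare. This stands, and it limits the size of the problem.

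**Counting outcomes as observed is legitimate.** A drop-out's Week 16 outcome is unknown; a prohibited-drug user's is known. A reader might call the two rules contradictory. They are not: counting the observed outcome is a treatment-policy choice that fits SAP 3.1.5. But the plan never states that choice, and under it the result no longer isolates the study drug.

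**The users are visible.** Deviations and concomitant medications are tabulated and listed, and the per-protocol exclusions are fixed before unblinding. This helps interpretation but does not change the primary result.

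**A blanket failure rule would be too wide.** The list in Protocol 5.6.1 includes high-dose acyclovir, valacyclovir and famciclovir. Failing every user would count patients treated for HSV or VZV as CMV failures. This stands and shapes the fix.

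**Conclusion.** The gap is real and modest. Under SAP 3.4.1, an event-free patient who starts a prohibited anti-CMV agent before Week 16 and remains in the study is a responder. The per-protocol analysis does not repair that in the mITT result.

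A reader might infer that the bias runs toward zero, because patients on placebo would have more low-level CMV to prompt treatment, and that power is therefore lost. The documents do not support a direction. If masking removes 10 points of events on placebo and 5 on NPC-21 (50% vs 25%), power at 48 per arm is 72.2%. If it removes 5 points from each arm (55% vs 25%), power is 86.3%, slightly above the 85.1% baseline. Use on NPC-21 alone inflates the effect.

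What can be said is that each such patient is worth about 2.1 points of an arm's rate, that equal use makes the choice of rule nearly irrelevant to power, and that use of 10% in one arm only separates the two rules by 10 points of difference. All of this rests on assumed frequencies of 0 to 10% and full suppression of events by the antiviral.

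**What to change.** Add to SAP 3.4.1: *patients who start an agent listed in Protocol 5.6.1 before Week 16 for prevention or treatment of CMV (by recorded indication), without CMV disease or viremia, are non-responders.* Show the present as-observed rule as a sensitivity analysis.

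The limit to a CMV indication keeps HSV and VZV treatment out of the failure count. No new data are needed: Protocol 5.6.3 already records drug name, dates and indication, and dosing for anti-CMV agents. The change affects classification in the analysis only, not patient management.

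For this dataset the timing matters. SAP version 1.0 was finalised on 29 March 2023 and the database was locked on 30 March 2023 (SAP Addendum, section 1). The new rule should therefore be reported only as a labelled post hoc sensitivity analysis, with the number of affected patients per arm, and the primary analysis left as it is.

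Cost: one sentence and one extra table. Event rates rise slightly in both arms, because some users would not have had CMV anyway. If use is equal between arms at 10%, power falls from about 78% to 76% before drop-outs are considered; with drop-outs counted as failures the two rules are within about one point.

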3.4.2 Secondary Efficacy Analysis

3.4.2.1 Categorical Endpoints

The categorical endpoints as below will be analyzed using the same analysis method as primary analysis:

- Incidence of CMV disease or CMV viremia by Week 28
- Incidence of CMV disease by Week 16
- Incidence of CMV disease by Week 28
- Incidence of CMV viremia by Week 16
- Incidence of CMV viremia by Week 28
- Incidence of anti-CMV therapy during the Rescue Phase

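### The addendum leaves the incidence of anti-CMV therapy in the Rescue Phase under an inherited drop-out rule which, read literally, counts untreated early leavers as events

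*SAP*

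**What the plan says.** SAP 3.4.2.1 introduces its list of six secondary endpoints with "The categorical endpoints as below will be analyzed using the same analysis method as primary analysis". The sixth item is "Incidence of anti-CMV therapy during the Rescue Phase". It has no week limit, denominator or drop-out rule of its own.

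SAP 3.4.1, the primary analysis, states as a matter of principle that "patients who discontinue from the study prior to Week 16 in the absence of CMV disease or CMV viremia will be considered as non-responders". It adds that an individual early leaver "may be discussed with the medical expert to determine status as a responder or non-responder".

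SAP Addendum 2.1 goes back to the list. It opens with "In SAP version 1.0, section 3.4.2.1 describes that the categorical endpoints are analyzed using the same analysis method as the primary endpoint" and then recalls that the primary analysis includes event-free early leavers among the non-responders. It decides as follows:

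- CMV disease by Weeks 16 and 28: "patients who discontinued from the study prior to Week 16 in the absence of CMV disease would not be considered as non-responders".
- CMV viremia by Weeks 16 and 28: leavers without "viremia would not be considered as non-responders".
- The Week 28 composite of the two keeps the rule, in these words: "the same analysis method as the primary endpoint is used by still including patients who discontinued from the study prior to Week 16".

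It does not mention the anti-CMV therapy endpoint. SAP 3.1.5 says that efficacy data are, in general, presented as observed without imputation. SAP 3.2.2 makes mITT the population for all efficacy analyses.

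**The concern.** Counting an event-free leaver as a failure is a recognised conservative choice when the question is whether prophylaxis worked. Whether an antiviral was given is a different kind of question. Within the study it is recorded: Protocol 5.6.3 requires dosing information for anti-CMV agents, and Protocol 6.6 has rescue entry logged with its date and reason. Consider a patient who withdraws at Week 6, never viremic and never given an antiviral. Under the inherited rule this patient would enter the numerator of an antiviral-use endpoint. The addendum dropped the rule even for disease and viremia taken singly, so it is hard to see why it should stay for drug use.

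The rate of antiviral use matters because Protocol 1 and 1.2 motivate NPC-21 partly by the toxicity of existing antivirals. A rate that mixes drug use with drop-out is hard to interpret, and a between-arm comparison could reflect nothing but unequal drop-out. It could also disagree with the counts of Rescue Phase entrants (SAP 3.3.1) and with the duration of rescue therapy (SAP 3.4.2.2), which has no value for an imputed recipient.

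**Working it through.** **The plan's own figure.** SAP 2.2.4 gives 48 per main arm for 60% versus 30%, two-sided 0.05, 80% power and 15% early discontinuation. With unpooled variance, n = (0.60×0.40 + 0.30×0.70) × (1.960 + 0.842)² / 0.30² = 39.2, rounded up to 40. Then 40/0.85 = 47.1, rounded up to 48. The stated figure is reproduced, and the point below does not affect it.

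**Matching the lists.**

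| Endpoint in SAP 3.4.2.1 | Decision in Addendum 2.1 |
|---|---|
| Disease or viremia, Week 28 | rule kept |
| Disease, Week 16 | rule removed |
| Disease, Week 28 | rule removed |
| Viremia, Week 16 | rule removed |
| Viremia, Week 28 | rule removed |
| Anti-CMV therapy in the Rescue Phase | none |

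Six endpoints inherit, five are decided and one is left. For the exploratory endpoints of SAP 3.4.3, Addendum 2.2 decides all four that inherit. The supportive central-PCR analysis there states its own drop-out rule. The anti-CMV therapy endpoint is therefore the only one left without a decision.

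**Size if the rule is followed literally.** Let d be the share of an mITT arm that leaves before Week 16 with no disease, viremia or antiviral, and p the share treated among the rest.

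- Recorded use = (1 − d) × p
- Counted under the inherited rule = (1 − d) × p + d
- Excess = d, whatever p is

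Assumptions: p = 30% (NPC-21) and 60% (placebo), borrowed from the primary endpoint's predicted incidences because the documents give no therapy rates. The value of d runs from 5% to 15%. The upper end is the plan's whole early discontinuation rate.

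| d, both arms | Patients per 48 | Recorded, NPC-21 vs placebo | Counted, NPC-21 vs placebo | Difference, recorded and counted |
|---|---|---|---|---|
| 5% | 2.4 | 28.5% vs 57.0% | 33.5% vs 62.0% | 28.5 points |
| 10% | 4.8 | 27.0% vs 54.0% | 37.0% vs 64.0% | 27.0 points |
| 15% | 7.2 | 25.5% vs 51.0% | 40.5% vs 66.0% | 25.5 points |

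With equal drop-out the difference does not move. The unadjusted odds ratio moves a little: at 15% it goes from (0.255/0.745)/(0.510/0.490) = 0.33 to (0.405/0.595)/(0.660/0.340) = 0.35.

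With unequal drop-out, the placebo-minus-NPC-21 difference shifts by (d placebo − d NPC-21):

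- 15% on NPC-21, 5% on placebo: recorded 57.0 − 25.5 = 31.5 points; counted 62.0 − 40.5 = 21.5 points.
- 5% on NPC-21, 15% on placebo: recorded 51.0 − 28.5 = 22.5 points; counted 66.0 − 33.5 = 32.5 points.

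**The case against.** A reader might infer that the plan says untreated leavers are counted as having received rescue therapy. It does not. SAP 3.4.1 defines a non-responder by CMV disease, viremia or early exit, not by treatment, and it allows case review. Protocol 6.6 lets rescue procedures take place whether or not an antiviral has been given. The rule therefore does not map cleanly onto drug use, and the consequence is an inference from inheritance. That limit stands.

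Second, the general as-observed rule in SAP 3.1.5 could be taken to govern here, with the inherited method meaning only the confidence intervals and the logistic model. The addendum weighs against this. If the general rule already blocked inheritance, the four exemptions would have been unnecessary, and it says the Week 28 composite still includes the leavers. For this one endpoint, however, the conflict is not expressly resolved.

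Third, if the denominator were only patients who entered the Rescue Phase, the excess would be zero, because entry requires disease or viremia. No document states that denominator, and mITT is specified for all efficacy analyses.

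Fourth, the 15% is a planning rate for early discontinuation and is not said to consist of event-free leavers before Week 16. A reader might also infer that the treatment comparison is necessarily biased. With equal drop-out the difference is unchanged.

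Finally, recorded use is not quite actual use. Treatment started after withdrawal may go unrecorded, and Protocol 4.3 foresees CMV treatment for some patients who leave because of COVID-19. This is a reason for a footnote but does not justify counting every leaver as treated. Rescue entry and concomitant medications are tabulated elsewhere, so a gross discrepancy would be visible.

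**Conclusion.** The point holds as a defect in one secondary endpoint. The text gives this endpoint a drop-out rule that does not suit it, and the addendum that reviewed that rule passed it over. Followed literally, with the mITT denominator, the rule raises each arm's reported rate by that arm's share of event-free, untreated leavers before Week 16. That is 5, 10 or at most about 15 points (roughly 7 of 48 patients) if such leavers are no more than the planned 15%. The between-arm difference changes only by the gap in drop-out, which is 10 points in the unequal examples and can go either way. The 30% and 60% treated shares are assumptions, but the size of the excess and of the shift does not depend on them. The documents do not show that the endpoint was actually tabulated this way, and the primary analysis is untouched.

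**What to change.** Add to Addendum 2.1 that the drop-out rule does not apply to this endpoint, and define it fully:

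- **Event:** at least one recorded dose of an anti-CMV agent during the Rescue Phase, through Week 28 or study exit.
- **Denominator:** all mITT patients.
- **Shown beside it:** by arm, the number who left before Week 16 untreated, with a note that therapy after withdrawal may not be recorded.

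The database was locked on 30 March 2023 and the addendum is dated 15 May 2023, so the change must be labelled as made after lock. The cost is a short paragraph, one changed derivation on data already collected, and a disclosed post-lock change to one secondary endpoint.
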